6.4.6.1.1. Sensitivity Analysis for Primary Efficacy Endpoints

In order to support the robustness of the conclusions drawn from the co-primary efficacy analyses, we will perform the following sensitivity analyses for the co-primary efficacy endpoints.

Percentage change in LDL-C from baseline to Day 510

• A control-based pattern-mixture model (PMM), using the same imputed datasets and MMRM model that was used for the second co-primary efficacy endpoint primary analysis will be used to compare treatments at Day 510. Multiple imputations will be

used to account for uncertainty in the imputation process and results from the imputed datasets will be combined using Rubin's method. (Refer to Appendix 3 for details)

- A mixed model for repeated measurements (MMRM) analysis without multiple imputation, that assumes missing data are missing at random (MAR), will be performed. The model will include fixed effects for treatment, visit, baseline value, and the interaction between treatment and visit. The Restricted Maximum Likelihood (REML) estimation approach will be used with the covariance structure set as "Unstructured". A linear contrast at Day 510 will be used to compare treatment groups. This will be the same model that is used as a sensitivity analysis for the second co-primary endpoint.
- The impact of country and current use of statins or other lipid-modifying therapies will be assessed by including country (possibly pooled into a region), the treatment-by-country interaction, and current use of statins or other lipid-modifying therapies (yes or no) as fixed effects into the primary efficacy analysis ANCOVA (using multiple imputation washout model data).
- An ANCOVA model without multiple imputation will be performed using the mITT population. The model will include the fixed effect of treatment group and baseline LDL-C as a covariate.
- A tipping point analysis will be performed to search for the tipping point that reverses the study conclusion. In the tipping point analysis, we will independently vary the deltas in the treatment groups (inclisiran group progressively worse while the placebo group is not impacted and inclisiran group progressively worse while the placebo group progressively improves) until the hypothesis test on the co-primary efficacy endpoint becomes statistically insignificant.

Time adjusted percentage change in LDL-C from baseline after Day 90 and up to Day 540.

- A mixed model for repeated measurements (MMRM) analysis without multiple imputation, that assumes missing data are MAR, will be performed. The model will include fixed effects for treatment, visit, baseline value, and the interaction between treatment and visit. The Restricted Maximum Likelihood (REML) estimation approach will be used with the covariance structure set as "Unstructured". A linear combination of the estimated means after Day 90 and up to Day 540 will be used to compare treatment groups. This will be the same model that is used as a sensitivity analysis for the first coprimary endpoint.
- The impact of country and current use of statins or other lipid-modifying therapies will be assessed by including country (possibly pooled into a region), the treatment-by-country interaction, and current use of statins or other lipid-modifying therapies (yes or no) as fixed effects into the primary efficacy analysis MMRM (using multiple imputation control-based PMM data).
- The time adjusted percentage change will also be calculated by taking the arithmetic mean of calculated percent change in LDL-C from baseline at each visit after Day 90 through Day 540. This analysis will be based on the control-based PMM imputed datasets (100 multiple imputation datasets). The two sample t-test will be performed to test the

treatment difference between inclisiran and placebo. Results will be combined and summarized using Rubin's method.

 A tipping point analysis will be performed to search for the tipping point that reverses the study conclusion. In the tipping point analysis, we will independently vary the deltas in the treatment groups (inclisiran group progressively worse while the placebo group is not impacted and inclisiran group progressively worse while the placebo group progressively improves) until the hypothesis test on the co-primary efficacy endpoint becomes statistically insignificant.

Other sensitivity analysis may be performed.

6.4.6.2. Secondary Efficacy Endpoints

The secondary efficacy endpoints will not be tested if either one of the co-primary efficacy endpoints' null hypothesis fails to be rejected.

The key secondary endpoints of this study are:

- Absolute change in LDL-C from baseline to Day 510.
- Time adjusted absolute change in LDL-C from baseline after Day 90 and up to Day 540.
- Percentage change from baseline to Day 510 in PCSK9, total cholesterol, ApoB, and non-HDL-C.

The Hochberg procedure [Hochberg, 1988] will be applied to control the family-wise type I error rate at a two-sided significance level of alpha=0.05 for the key secondary endpoints.

Missing values will be imputed using the control-based PMM (see Appendix 2 for more details) on LDL-C, PCSK9, total cholesterol, ApoB, and non-HDL-C, absolute change or percent change from baseline will be calculated based on imputed data before any analysis is performed.

The absolute change in LDL-C from baseline to Day 510 and percentage change from baseline to Day 510 in PCSK9, total cholesterol, ApoB, and non-HDL-C will be analyzed using a MMRM with covariates as specified in Appendix 1 and Appendix 3. Time adjusted absolute change in LDL-C from baseline after Day 90 and up to Day 540 will be analyzed similarly to that of time adjusted percentage change in LDL-C from baseline after Day 90 and up to Day 540.

MMRM without multiple imputation (see Appendix 1) will be used as sensitivity analyses for the key secondary endpoints.

The other secondary endpoints of this study are:

- Maximum percentage change in LDL-C. This is calculated by finding the smallest LDL-C value across all post baseline visits for each individual subject. This value will be used to compare with each subject's baseline value and calculate the percent change from baseline to the lowest LDL-C value.
- Absolute change from baseline to Day 510 in PCSK9, total cholesterol, ApoB and non-HDL-C.

- Absolute change and percentage change in LDL-C from baseline to each assessment time up to Day 540.
- Individual responsiveness defined as the number of subjects reaching on treatment LDL C levels of <25 mg/dL, <50 mg/dL, <70 mg/dL, and <100 mg/dL at Day 510.
- Proportion of subjects in each group with greater or equal to 50% LDL-C reduction from baseline.
- Absolute change and percentage change in other lipids, lipoproteins, apolipoproteins, and PCSK9 from baseline at each subsequent visit to Day 540.
- Proportion of subjects in each group who attain global lipid targets for their level of ASCVD risk.

The two-sided 95% confidence interval for least squares means will be provided for continuous variables at a single point using an analysis of covariance model or using MMRM methods for variables measured over time (see Appendix 1 for more details). The odds ratio and 95% confidence interval for the odds ratio will be provided for binary variables using logistic regression models. Nominal p-values will be provided when applicable.

Descriptive and graphical summaries by treatment group will also be presented.

6.4.6.3. Exploratory Endpoints

The exploratory endpoints of this study are:

- Incidence of CV death, resuscitated cardiac arrest, non-fatal MI, and stroke (ischemic and hemorrhagic)
 - A major cardiovascular event (MACE) is defined as the composite of CV death, resuscitated cardiac arrest, non-fatal MI, and stroke (ischemic or hemorrhagic). Refer to Appendix 5 for details on the search terms used. The number and percentage of subjects with MACE or any of the individual events will be presented by treatment group.
- Proportion of subjects in each group with any LDL-C reduction from baseline at any visit (responders).
 - The number and percentage of subjects with any LDL-C reduction at any visit will be presented by treatment group. The odds ratio and 95% confidence interval for the odds ratio will be provided using a logistic regression model. The number and percentage of subjects with any LDL-C reduction will also be summarized at each visit.
- Response of LDL-C reduction by underlying causal mutations of HeFH

The absolute change and percentage change in LDL-C and PCSK9 from baseline to Day 510 will be summarized by HeFH mutation type and treatment group.

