6. STATISTICAL PLAN

6.1. Sample Size

The sample size calculation is performed with the assumption (which is based on the observed results from a Phase II study) that the difference in change from baseline between the active dose group and the placebo group for LDL-C will be no less than 30 mg/dL, with a standard deviation of 20 mg/dL.

Assuming about a 5% drop out rate, the sample size will be approximately 380 subjects that are evaluable for efficacy across the placebo and inclisiran dose groups. This sample size of at least 380 evaluable subjects, will provide more than 90% power to detect a 30% reduction of LDL-C levels in the inclisiran group compared to the placebo group at one-sided significance level of 0.025. Due to faster than expected enrollment, actual enrollment was 482 subjects. This increased sample size will contribute additional safety data and not appreciably affect power calculations.

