6.3.3. Analysis Windows and Baseline

The analysis windows around each visit day are provided in Table 2: below.

Table 2: Analysis Windows for Each Scheduled Visit

Scheduled Visit	Analysis Window	
	From To	
Baseline		Before randomization/First Study Treatment
Day 30	Day 1	Day 60
Day 90	Day 61	Day 120
Day 150	Day 121	Day 210
Day 270	Day 211	Day 300
Day 330	Day 301	Day 390
Day 450	Day 391	Day 480
Day 510	Day 481	Day 525

Day 540 Day 526	No upper limit
-----------------	----------------

Data collected at scheduled or unscheduled visits will be used in the analysis if they fall into an analysis window for a scheduled visit. If more than one visit (scheduled or unscheduled) is made within the window specified above for any scheduled visit, the non-missing assessment closest to the scheduled visit day will be used in the analysis for that visit. However, all data will be included in the subject data listings.

Unless otherwise specified, data collected from assessments that occur more than once prior to initiation of investigational product administration, the latest assessment will be considered the "Baseline" evaluation for analysis.

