8. CHANGES TO ANALYSES SPECIFIED IN THE PROTOCOL

The following items were changed between the final version of the protocol and the final SAP.

- Primary efficacy endpoint analyses were modified per FDA feedback.
- Due to the distribution of the data, current use of statins or other lipid-modifying therapies at baseline (yes or no) was removed from the primary analyses and included as factors in the models of the sensitivity analyses.
- Imputation methods were modified per FDA feedback.
- Subgroup analyses were added for select variables.
- A secondary efficacy endpoint was renamed from mean maximum percent change to maximum percent change.
- The exploratory endpoint, proportion of subjects in each group with any LDL-C reduction from baseline at any visit (responders), was added
- Identification of PCS/CS laboratory values were modified.

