APPENDIX 1. DETAILS OF MMRM USED FOR EFFICACY ANALYSES

A number of efficacy analyses will utilize a mixed-effects model for repeated measures (MMRM). This includes the co-primary efficacy endpoints (in the case of the first co-primary efficacy endpoint, it will be used as a sensitivity analysis), the key secondary efficacy endpoints, and other secondary efficacy endpoints.

The models will generally include fixed effects for treatment, visit, baseline value, and the interaction between treatment and visit. The current use of statins or other lipid-modifying therapies will also be included as a fixed effect for some sensitivity analyses. The visits will include Days 90, 150, 270, 330, 450, and 510, with Day 510 as the primary time-point. Linear combinations of the estimated means will be created for the various hypothesis tests. Note that for time adjusted percentage change analyses (second co-primary efficacy endpoint) Day 90 will be excluded from the models.

The Restricted Maximum Likelihood (REML) estimation approach will be used with the covariance structure set as "Unstructured." The least squares means will be calculated for each treatment at each visit.

The analysis will be carried out using the SAS PROC MIXED procedure.

Sample SAS statements follow:

```
ods output LSmeans=estimates;
ods output Diffs=lsdiffs;
Proc Mixed Data=ldl_data;
   Class treatment visit_day subject_id;
   Model percent_change = treatment|visit_day base_value/DDFM=KR;
repeated visit_day/type=UN subject=subject_id;
LSMeans treatment*visit_day/cl pdiff=control('0' '510');
run;

(where ('0' '510') is the value of the placebo ['0'] at day 510 ['510'] in interaction term treatment*visit_day)
```

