APPENDIX 3. CONTROL-BASED PATTERN MIXTURE MODEL

A control-based Pattern-Mixture Model (PMM) will be used to explore the possibility of data missing not at random (MNAR) for subjects who discontinued the study. For subjects who discontinued the study without any further follow-up data, their missing values after study discontinuation will be imputed under the assumption that their outcome would be the similar to those in the placebo group with similar background characteristics. For subjects who did not discontinue the study, their intermittent missing values will be imputed based on the MAR assumption. Multiple imputation will be used to account for uncertainty in the imputation process and results from the imputed datasets will be combined using Rubin's method. Further details are provided below.

Windowing will be performed first (see Section 6.3.3) and any missing data will be imputed using the following steps.

The covariates and baseline characteristics which can be predictive of the response will be included in a multiple imputation procedure (SAS PROC MI) and will include the following:

- Baseline value of efficacy measurement (continuous)
- Observed value of efficacy measurement at Day 90 (continuous)
- Observed value of efficacy measurement at Day 150 (continuous)
- Observed value of efficacy measurement at Day 270 (continuous)
- Observed value of efficacy measurement at Day 330 (continuous)
- Observed value of efficacy measurement at Day 450 (continuous)
- Observed value of efficacy measurement at Day 510 (continuous)
- Observed value of efficacy measurement at Day 540 (continuous)
- Current use of statins or other lipid-modifying therapies (categorical)
- 1. Intermittent missing data will be imputed using MCMC methods, assuming MAR, within each treatment group. SAS PROC MI will be utilized for this step using the MCMC impute=monotone option. A total of 100 datasets will be created. These datasets will be utilized in Step #2.

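### The exploratory responder endpoint counts any LDL-C fall at any of seven visits, so most placebo subjects qualify by chance and the planned odds ratio may be infinite or uninformative

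*SAP*

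**What the plan says.** SAP section 6.4.6.3 lists among the exploratory endpoints "Proportion of subjects in each group with any LDL-C reduction from baseline at any visit (responders". It sets no minimum reduction, no fixed visit and no requirement that the reduction persist. For the analysis it states that "The odds ratio and 95% confidence interval for the odds ratio will be provided using a logistic regression model", and it adds that "The number and percentage of subjects with any LDL-C reduction will also be summarized at each visit". It names no method for an empty or very small cell, and neither does the general rule for binary variables in section 6.4.6.2.

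The endpoint is not in protocol section 3.5. SAP section 8 records that the "proportion of subjects in each group with any LDL-C reduction from baseline at any visit (responders), was added", so the SAP text is its whole specification.

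The number of looks comes from the visit schedule. SAP Appendix 1 states: "The visits will include Days 90, 150, 270, 330, 450, and 510, with Day 510 as the primary time-point". Appendix 3 adds "Observed value of efficacy measurement at Day 540 (continuous" to the imputation variables, and SAP Table 1 schedules a fasting lipid profile at that visit and none at Day 30. That makes seven scheduled post-baseline LDL-C values. Baseline is a single value: where several pre-dose assessments exist, section 6.3.3 says "the latest assessment will be considered the" baseline.

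**The concern.** A subject who does not respond at all still has LDL-C values that move up and down around a personal level. Asking whether any one of seven later values falls below a single baseline value, by any amount, gives that subject seven chances to qualify. A placebo responder rate of two-thirds or more could then appear in the report with no effect behind it, and a reader who takes the word at face value would be misled about individual response in both arms.

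The same rule causes an estimation problem. If nearly all inclisiran subjects qualify, the inclisiran non-responder cell may be empty. The logistic model then has quasi-complete separation: the maximum-likelihood odds ratio is infinite and the usual confidence interval cannot be computed.

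**Working it through.** **Inputs from the documents.** There are seven post-baseline lipid visits and one baseline value. Enrolment was 482, so 482 / 2 = 241 per arm if the planned 1:1 allocation held. SAP section 6.1 assumes that the difference "for LDL-C will be no less than 30 mg/dL, with a standard deviation of 20 mg/dL". Protocol section 1.2.2.2 reports a mean LDL-C reduction of around 50% after one 300 mg dose.

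**Assumed, because the documents do not give them.** The correlation rho between a subject's change scores, any placebo drift, and the SD of percentage change.

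**The plan's own figure.** The SAP states no figure for this endpoint. Its power statement does reproduce: 400 × 0.95 = 380, or 190 per arm. With difference 30 and SD 20 the standardised effect is 1.5, and 1.5 × √(190/2) − 1.96 = 12.7, so power exceeds 0.9999. The stated figure of more than 90% is met.

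**Step 1: placebo rate with no effect.** If baseline and the seven later values are exchangeable, baseline is the lowest of the eight with probability 1/8. The chance of qualifying is 1 − 1/8 = 87.5%.

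For normal change scores with common correlation rho and mean shift m in SD units,

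P(qualify) = 1 − ∫ φ(u) Φ((m + √rho·u)/√(1 − rho))^7 du.

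Exchangeable values correspond to rho = 0.5 and m = 0.

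| rho | no drift | upward drift of 0.25 SD |
|---|---|---|
| 0.5 | 87.5% | 80.1% |
| 0.6 | 83.7% | 75.6% |
| 0.7 | 79.3% | 70.6% |
| 0.8 | 74.0% | 64.7% |
| 0.9 | 67.0% | 57.3% |

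Serially correlated levels at the actual visit days, without drift, give 79% to 85%. One fixed visit without drift gives 50% whatever the correlation; the excess over 50% comes from taking the best of seven.

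**Step 2: inclisiran non-responders over seven visits, n = 241.** The same formula with a negative shift gives p, the chance that all seven values are at or above baseline. The chance of an empty cell is (1 − p)^241.

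| Assumption | rho 0.5 | rho 0.7 | rho 0.8 |
|---|---|---|---|
| Difference 30, SD 20: expected non-responders | 0.3 | 1.5 | 2.9 |
| Difference 30, SD 20: chance of none | 73% | 22% | 5% |
| 50% reduction, SD 20 points (assumed): chance of none | 99.7% | 96% | 90% |
| 50% reduction, SD 30 points (assumed): chance of none | 85% | 41% | 16% |

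At rho = 0.9 the three chances are 0.3%, 74% and 2%.

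**Step 3: a nearly empty cell.** Take 1 of 241 inclisiran non-responders against 48 of 241 on placebo. The odds ratio is (240 × 48)/(1 × 193) = 59.7. The SE of its logarithm is √(1/240 + 1/1 + 1/193 + 1/48) = 1.015, so the 95% interval is about 8 to 436. It is finite but says little about size.

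**Step 4: one fixed visit instead.** With 30/20, the non-responder chance is Φ(−1.5) = 6.7%, or 16 of 241, and an empty cell is practically excluded. With a 50% reduction and SD 20, it is Φ(−2.5) = 0.62%, or 1.5 of 241, and the chance of none is (1 − 0.0062)^241 = 22%. The risk falls sharply but does not vanish.

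**The case against.** A reader might infer that the endpoint cannot tell drug from noise. The figures do not support that. With 0 of 241 inclisiran non-responders against 30 of 241 on placebo (12.5%), Fisher's exact test gives p of about 7 × 10⁻¹⁰. Results are presented by treatment group, so the concurrent placebo column shows how often chance alone qualifies a subject. The comparison works; what fails is the reading of the absolute rates and of the label for an individual subject.

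A reader might also take a figure such as 87.5% as established. It follows from exchangeability, which the documents neither state nor contradict. Other correlations and drifts move it widely, and placebo subjects here are on background lipid-lowering therapy, not untreated.

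Three further points stand in the plan's favour. The endpoint is exploratory and lies outside the nested and Hochberg testing. SAP section 6.4.6.2 already plans stricter response measures, including a reduction of at least 50% and attainment of fixed LDL-C levels at Day 510. By-visit counts, which include Day 510, are already planned.

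It is also true that a zero threshold at Day 510 still labels about half of placebo subjects as responders when there is no effect. That change removes the best-of-seven excess and eases the empty cell; it does not make the threshold clinically meaningful.

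Finally, an empty cell is not certain. Early dropouts with only one or two samples could leave a few inclisiran non-responders and a finite, unstable estimate.

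**Conclusion.** The point holds as a low-priority improvement. Without any effect, the any-visit rule would label 87.5% of placebo subjects responders under exchangeability. The rate is 67% to 88% for rho of 0.5 to 0.9 without drift, and 65% to 80% for rho of 0.5 to 0.8 with upward drift of 0.25 SD. Both together at rho = 0.9 would lower it to 57%. All but the first figure rest on assumptions that the documents do not supply.

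For rho of 0.5 to 0.8, the chance of an empty inclisiran non-responder cell is 5% to 73% under the SAP's planning values and 90% or more under a 50% reduction with an assumed SD of 20 points. The SAP gives no fallback for that case.

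A reader might infer that the trial's efficacy conclusions are weakened, or that the endpoint was introduced after unblinding. Neither follows. No co-primary or key secondary test uses this endpoint. The addendum's introduction places finalisation of the SAP ahead of its post-unblinding changes, and those changes do not include this endpoint.

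**What to change.** Rewrite the one bullet in SAP section 6.4.6.3:

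- Base the responder odds ratio on a single fixed measurement, LDL-C below baseline at Day 510, and state beside it that 50% is the no-effect placebo reference when there is no drift.
- Name Firth or exact logistic regression as the method when a cell is empty or sparse.
- Keep the by-visit counts. Report the any-visit proportion, if wanted, descriptively and without the responder label, and point to the existing endpoint of at least 50% reduction for meaningful response.
- Say how a subject without a Day 510 value is counted, because section 6.3.4.1 leaves endpoints of this rank unimputed and excluded.

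The cost is one SAP paragraph and the redefinition of one exploratory endpoint, with subjects lacking a Day 510 value dropping out unless a rule is given. The addendum was written after database lock and unblinding, so a change made now must be labelled post hoc. The any-visit result as originally specified should then be reported alongside it for transparency, with the caveat about best-of-seven inflation.
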